3.1.1 DNAD Participants

On Day 7, DNAD participants will begin applying triamcinolone 0.1% ointment (provided by the study) twice daily to the specified target area. Additionally, DNAD participants will apply triamcinolone 0.1% ointment (non-sensitive regions)/ hydrocortisone 2.5% ointment (sensitive regions) twice daily to active lesions on non-target skin.

On Day 35, DNAD participants will return for a 4 Week Steroid Assessment, where response to triamcinolone will be evaluated at the target site by TAA and targeted EASI scoring, and overall management of AD body-wide by topical steroid/moisturizer treatment will be evaluated by EASI score. DNAD participants who have an inadequate body-wide response to topical steroid/moisturizer treatment (EASI > 7) will be designated as "topical steroid non-responders" and will begin treatment with dupilumab. DNAD participants with EASI ≤ 7 will be designated as "topical steroid responders" and will continue to apply triamcinolone/hydrocortisone to active lesions.

Topical Steroid Responders

After the 4 Week Steroid Assessment, topical steroid responders will discontinue applying triamcinolone 0.1% ointment to non-lesional skin on the target area. Topical steroid responders will begin to apply triamcinolone 0.1% ointment (non-sensitive regions)/ hydrocortisone 2.5% ointment (sensitive regions) once or twice daily, per clinician discretion, to active lesions body-wide. They will return for up to three additional scheduled visits prior to their End of Study Visit: an Optional Steroid Assessment, 12 Week Steroid Assessment, and a 19 Week Steroid Assessment.

If symptoms worsen at any time between planned study visits, participants can be scheduled for an Unscheduled Visit. If their EASI score is > 7 at any of the scheduled or unscheduled visits beginning at the 4 Week Steroid Assessment through the 12 Week Steroid Assessment, they will be designated as a “topical steroid non-responder” and will begin treatment with dupilumab. After the 12 Week Steroid Assessment, if the participant’s EASI score is > 7 at any point, they will be withdrawn from the study.

[figure not shown]

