Assuming a prevalence of 50% for type 2-high status, as well as the group-level sample sizes in Table 13.7.1.1, we have 80% power to detect statistical significance for the odds ratios listed in the table below (we also provide calculations assuming 5% dropout after the first week). Power was calculated based on simple logistic regression with a binary predictor assuming an alpha level of 0.05 ([Hsieh et al, 1998](#)).

Table 13.7.1.1 Power justification of the Primary Objective in adults and children

Population	Comparison	Comparison group sample size	Reference group sample size	Minimum detectable odds ratio at 80% power	
				Assuming target sample size	Assuming 5% dropout
Adults	AD vs. Non-AD	260	100	1.95	1.99
	Moderate-to-severe AD vs. Mild AD	160	100	2.06	2.10
Children	AD vs. Non-AD	130	50	2.60	2.68
	Moderate-to-severe AD vs. Mild AD	80	50	2.80	2.89

Additionally, Figure 13.7.1.1 displays a range of power scenarios for these comparisons of interest.

Figure 13.7.1.1 Power curves for association tests in the Primary Objective

Note that the primary objective includes Day 7 data only, and therefore will not be impacted by participant dropout during the study.

Power analysis for Secondary Objective #1

SO1 is as follows: to determine how gene expression in the skin (skin tape) differs between non-AD participants and those with current mild or moderate-to-severe AD disease.

[figure not shown]
Assuming a gene expression coefficient of variation (CV) of 0.4 to approximate the observed median CV value across genes in humans ([Hart et al, 2013](#)), as well as the group-level sample sizes in Table 13.7.1.2, we have 80% power to detect statistical significance for the fold changes listed in Table 13.7.1.2. Power was calculated using the RNA-seq power computation method of [Hart et al, 2013](#). The significance threshold (α) was set at 0.05/10,000, assuming ~10,000 expressed genes with sufficient variability to test. Finally, we assumed the least powerful situation for identifying differential expression, which is for genes that are lowly expressed (10 reads per gene). We calculated power assuming both our target sample sizes as well as for the case of 20% dropout by end of study.

Table 13.7.1.2 Power justification of Secondary Objective #1 in adults and children

				Minimum detectable fold change at 80% power	
Population	Comparison	Comparison group sample size	Reference group sample size	Assuming target sample size	Assuming 20% dropout

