Adults	AD vs. non-AD	260	100	1.38	1.44
	Mild AD vs. non-AD	100	100	1.48	1.55
	Moderate-to-severe AD vs. non-AD	160	100	1.42	1.48
	Moderate-to-severe AD vs. Mild AD	160	100	1.42	1.48
Children	AD vs. non-AD	130	50	1.58	1.67
	Mild AD vs. non-AD	50	50	1.74	1.85
	Moderate-to-severe AD vs. non-AD	80	50	1.64	1.74
	Moderate-to-severe AD vs. Mild AD	80	50	1.64	1.74

Additionally, Figure 13.7.1.2 displays a range of power scenarios for these comparisons of interest.

Figure 13.7.1.2 Power curves for differential expression analyses in SO1. A) Assuming target sample sizes. B) Assuming sample sizes after 20% dropout by end of study.

Note that SO1 will assess differences in gene expression at both Day 7 and End of Study (Day 168-224).

Power analysis for Secondary Objective #2

SO2 is as follows: to determine how gene expression in the skin (skin tape) changes over time among the study outcome groups: (1) topical steroid responders, (2) dupilumab responders, (3) dupilumab non-responders, (4) non-AD, and (5) long-term dupilumab participants.

[figure not shown]
Anticipated group sample sizes are based on the targeted population sample sizes and assumed treatment response rates described in [Section 13.7.1](#). The method for power calculation and underlying assumptions (gene expression CV, alpha, etc.) were identical to those used for SO1. Based on these assumptions, we have 80% power to detect statistically significant fold changes in gene expression between the study start and end points for the groups and fold changes listed in Table 13.7.1.3. Again, we calculated power for both our target samples sizes as well as for the case of 20% dropout by end of study.

Table 13.7.1.3 Power justification for Secondary Objective #2 in adults and children

Population	Study outcome group	Sample size	Minimum detectable fold change at 80% power	
			Assuming target sample size	Assuming 20% dropout
Adults	Topical steroid responders	175	1.34	1.39
	Dupilumab responders	34	1.95	2.11
	Dupilumab non-responders	51	1.73	1.84
	Non-AD	100	1.48	1.55
	Long-term dupilumab	40	1.85	1.99
Children	Topical steroid responders	87	1.52	1.60
	Dupilumab responders	17	2.57	2.88
	Dupilumab non-responders	26	2.15	2.35
	Non-AD	50	1.74	1.85
	Long-term dupilumab	20	2.39	2.65

Additionally, Figure 13.7.1.3 displays a range of power scenarios for these expression changes of interest.

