6.2 Disposition of Subjects

Study participants, whether child or adult, will be allocated to the following diagnostic groups prior to analysis:

- I. *Non-AD*
Participants never diagnosed with AD.
- II. *Dupilumab-naïve AD participants*
AD participants never taking dupilumab.

There are two possible AD severity groups:

1. Mild AD (EASI ≤ 7 at analysis timepoint)
2. Moderate-to-severe AD (EASI > 7 at analysis timepoint)

There are three possible outcome groups:

1. Topical steroid responders: Those on topical steroid who never obtain an EASI score > 7 by the 12-Week Steroid Assessment visit (EASI score > 7 obtained after that point will lead to early study termination).
2. Dupilumab responders: Steroid non-responders on dupilumab who obtain an EASI score ≤ 7 at the 15-Week Dupilumab Assessment visit (regardless of EASI scores obtained before or after that visit).
3. Dupilumab non-responders: Those on dupilumab who fail to obtain an EASI score ≤ 7 at the 15-Week Dupilumab Assessment visit (regardless of EASI scores obtained before or after that visit).

- III. *Long-term dupilumab AD participants*
AD participants already on dupilumab (for ≥ 4 months) at the start of the study. These patients will continue dupilumab treatment as prescribed by their physician outside of the study.

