Although the above analyses will focus on non-lesional skin samples, which will be available for all participants, we will also examine differences in disease signatures between lesional and non-lesional skin in participants from whom we have both types of samples (AD participants only) using a linear mixed model. Variance stabilizing transformation (VST)-normalized gene expression (Love et al. 2014) will be used as the outcome and models will include fixed effects for skin type (lesional or non-lesional), disease severity (mild or moderate-to-severe), and skin type x disease severity interaction, along with a random intercept for each participant to account for pairing of lesional and non-lesional samples. The interaction term will allow us to explicitly test for different changes between mild and moderate-to-severe AD in lesional vs. non-lesional skin. Using this model, we will also be able to compare gene expression differences between disease groups within lesional skin. Note that each of the above models will be fit for each visit separately. The above models will also be fit separately for children and adults, after which we will fit a combined model using interaction terms with age group to identify severity changes that are shared and unique to age groups.

In total, there will be 22 distinct models:

Response	Population	Regressors	Model #
Single-gene differential expression from Non-lesional STS collected at Day 7	Adults (18+ year olds)	Non-AD vs. DNAD (all severity) at Day 7	1
		Non-AD vs Mild DNAD at Day 7	2*
		Non-AD vs Moderate-to-Severe DNAD at Day 7	3*
		Mild vs. Moderate-to-Severe DNAD at Day 7	4
	Children (6-17 year olds)	Non-AD vs. DNAD (all severity) at Day 7	5
		Non-AD vs Mild DNAD at Day 7	6*
		Non-AD vs Moderate-to-Severe DNAD at Day 7	7*
		Mild vs. Moderate-to-Severe DNAD at Day 7	8
Single-gene differential expression from Non-lesional STS collected at End of Study (Day 168-224)	Adults (18+ year olds)	Non-AD vs. DNAD (all severity) at End of Study	9
		Non-AD vs Mild DNAD at End of Study	10*
		Non-AD vs Moderate-to-Severe DNAD at End of Study	11*
		Mild vs. Moderate-to-Severe DNAD at End of Study	12
	Children (6-17 year olds)	Non-AD vs. DNAD (all severity) at End of Study	13
		Non-AD vs Mild DNAD at End of Study	14*
		Non-AD vs Moderate-to-Severe DNAD at End of Study	15*
		Mild vs. Moderate-to-Severe DNAD at End of Study	16

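### SO1's End-of-Study power figures use the enrolment severity groups, but the analysis groups by EASI at that visit, where about 41 adults rather than 128 are projected to be moderate-to-severe

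*Protocol*

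**What the plan says.** Protocol section 13.7.1 gives minimum detectable fold changes for SO1 in Table 13.7.1.2 and states that "we have 80% power to detect statistical significance for the fold changes listed in Table 13.7.1.2". The group sizes are the enrolment targets: 160 moderate-to-severe, 100 mild and 100 non-AD adults, and 80, 50 and 50 children. A second column covers End of Study: "We calculated power assuming both our target sample sizes as well as for the case of 20% dropout by end of study". The section adds: "Note that SO1 will assess differences in gene expression at both Day 7 and End of Study (Day 168-224".

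The analysis does not group by enrolment severity. Protocol section 13.6.2 tests SO1 by current severity, separately at each visit. SAP section 6.2 defines the upper group as "Moderate-to-severe AD (EASI > 7 at analysis timepoint". SAP section 5.2 puts Day 168-224 in the first secondary estimand, and section 9.2.1 marks model 11 (adults) and model 15 (children), "Non-AD vs Moderate-to-Severe DNAD at End of Study", among those that answer SO1.

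Between the two visits the design sorts participants by EASI. Under Protocol section 3.1.1, steroid-treated participants whose EASI exceeds 7 from the 4-week through the 12-week visit start dupilumab. After the 12-week visit, if a steroid-treated participant's EASI "score is > 7 at any point, they will be withdrawn from the study". A footnote to the flow chart limits that withdrawal to the time before the End of Study visit.

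**The concern.** The power table and the analysis use different severity groups at End of Study. The table carries the enrolment split forward and shrinks it by 20%. The treatment pathway instead empties the moderate-to-severe group of steroid users, so on plan it consists of participants who received dupilumab and did not respond. The same section projects how many these are and uses the numbers for SO2 in Table 13.7.1.3, but not for SO1 at the same visit.

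Two things are at stake. The stated sensitivity of the End-of-Study moderate-to-severe contrasts, two of which carry the SO1 estimand (models 11 and 15), is too favourable. And a severity difference at that visit is partly a difference in treatment received, which the SO1 models do not have to account for.

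**Working it through.** **Inputs, all from Protocol section 13.7.1 unless noted.** CV 0.4; depth 10 reads per gene; power 80%; the threshold "was set at 0.05/10,000, assuming ~10,000 expressed genes with sufficient variability to test", so alpha = 0.000005. Sidedness is not stated. Steroid failure is 50% of moderate-to-severe and 5% of mild participants; about 40% of dupilumab starters reach EASI of 7 or less.

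**Formula for the cited RNA-seq method, two-sided.** FC = exp{(z₁₋α/₂ + z₀.₈) × √[(1/10 + 0.4²)(1/n₁ + 1/n₂)]}, with z values 4.565 + 0.842 = 5.406.

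**Reproducing the stated figures.**
- 160 vs 100 adults: 1.421 (stated 1.42).
- 128 vs 80 adults: √(0.26 × 0.02031) = 0.0727; exp(5.406 × 0.0727) = 1.481 (stated 1.48).
- 64 vs 40 children: 1.743 (stated 1.74).

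All SO1 rows match to rounding. A one-sided test does not match (1.465 for 128 vs 80). The 20% column is therefore 0.8 × the enrolment groups.

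**Groups expected at End of Study on the protocol's own rates.**
- Adult dupilumab starters: 0.50 × 160 + 0.05 × 100 = 85. Non-responders: 0.6 × 85 = 51; responders: 34; steroid responders: 260 − 85 = 175. These are the sizes in Table 13.7.1.3.
- After 20% dropout: moderate-to-severe 0.8 × 51 ≈ 41; mild 0.8 × (175 + 34) ≈ 167; non-AD 80.
- Children (Table 13.7.1.3: 87, 17 and 26): moderate-to-severe 0.8 × 26 = 20.8; mild 0.8 × (87 + 17) = 83.2; non-AD 40.

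**Adults: detectable fold change, with power at 1.48 in brackets.**

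| Case at End of Study | Mod.-severe / mild | vs non-AD (80) | vs mild |
|---|---|---|---|
| Table as printed | 128 / 80 | 1.48 (80%) | 1.48 (80%) |
| Protocol's own rates | 41 / 167 | 1.70 (29%) | 1.62 (44%) |
| Plus 5% of 140 steroid responders first above 7 at this visit | 48 / 160 | 1.65 (36%) | 1.57 (54%) |
| Plus 10% of them | 55 / 153 | 1.62 (43%) | 1.54 (63%) |
| All dupilumab-treated above 7 (0.8 × 85) | 68 / 140 | 1.58 (54%) | 1.50 (74%) |
| Treatment failures leave early | 30 / 167 | 1.80 (17%) | 1.73 (25%) |

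The 5%, 10% and 30-participant cases are assumptions. Only an extreme combination, all dupilumab-treated adults plus 10% of steroid responders (68 + 14 = 82 vs 126 mild), brings the comparison with mild back to 1.48. Against non-AD it still gives 1.54 (63%).

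**Children.** Moderate-to-severe vs non-AD: 2.11 (stated 1.74; power at 1.74 about 29%). Vs mild: 1.97 (stated 1.74; about 45%). If all dupilumab-treated children exceed 7 (0.8 × 43 = 34.4, against 40 non-AD or 0.8 × 87 = 69.6 mild): 1.90 (54%) and 1.78 (74%).

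**What gains or stays the same.** Mild vs non-AD improves: about 1.46 in adults (stated 1.55) and 1.70 in children (stated 1.85). Pooled AD is 41 + 167 = 208 = 0.8 × 260, so that row is unchanged. Day 7 figures are untouched.

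**Confounding.** On the projected counts every moderate-to-severe participant has had dupilumab, while 175/209 = 84% of mild adults are steroid-only. If 5% of steroid responders first exceed 7 at the final visit, 41/48 = 85% of the moderate-to-severe adults are dupilumab-treated. A comparison within dupilumab-treated participants is possible: 0.8 × 34 = 27.2 vs 0.8 × 51 = 40.8 adults gives 1.98; 13.6 vs 20.8 children gives about 2.6.

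**The case against.** **The count of 41 is a projection.** This stands. The SAP fixes dupilumab response at the 15-week visit whatever EASI is later, and End of Study falls 133 − 105 = 28 days afterwards, once dupilumab has ended. Relapse would raise the count, steroid users may first exceed 7 at the last visit, and early exits for treatment failure would lower it. A reader might take 41 as the delivered sample size; the documents support only a range around it.

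**The power assumptions are deliberately harsh.** Also true: 10 reads, and a Bonferroni-type threshold where SAP section 9.2.1 uses a 5% false discovery rate. At 50 reads (an assumption), 41 adults would give power of about 59% against non-AD and 77% against mild at 1.48. But the same change lifts 128 vs 80 to about 97%, so the mismatch in group size remains.

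**The sample size rests on the primary comparison at Day 7.** Correct, and that comparison is untouched. The SO1 table is still a stated justification.

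**Treatment path is partly handled.** SAP section 8.2 allows concomitant therapies as a covariate, the 22 SO1 models are repeated with covariates, SO2 contrasts outcome groups over time, and exploratory objective 6 compares them at each visit. This reduces the concern but does not remove it: the covariate is optional and no SO1 model requires a treatment-path term.

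**Stronger readings.** A reader might infer that severity and dupilumab exposure cannot be separated at all. The documents do not support that, because 34 adult dupilumab responders are expected in the mild group. Nor do they require the End-of-Study models to become supportive: both visits belong to the SO1 endpoint and estimand, so demotion would change the role of a stated endpoint.

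**Conclusion.** The End-of-Study column of Table 13.7.1.2 is wrong as written for the moderate-to-severe rows. Its arithmetic is right for its inputs, but the inputs do not describe the groups that SO1 will compare at that visit.

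The central figures rest on the protocol's projected response rates, on the 15-week response carrying over to End of Study, and on 20% dropout applied equally to all groups. Relaxing the second assumption narrows the gap: with every dupilumab-treated adult above 7, the comparison with mild comes close to the stated value. The comparison with non-AD stays well short of 80% power at 1.48 in every case examined. The effect runs in both directions, since the mild against non-AD rows are understated.

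Confounding of severity with treatment path at End of Study is heavy but incomplete, and a larger sample would not remove it. SO1 at Day 7 and the primary objective are not in question.

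**What to change.** 1. In Protocol section 13.7.1, rebuild the End-of-Study column of Table 13.7.1.2 from the outcome-group sizes in Table 13.7.1.3. Give a range for the moderate-to-severe count, state the assumption about EASI between the 15-week and final visits, and show the rows that gain as well as those that lose.
2. In SAP section 9.2.1, for mild against moderate-to-severe at End of Study (models 12 and 16), add a treatment-path term or a comparison within dupilumab-treated participants, with its limited sensitivity stated.
3. Report the End-of-Study non-AD contrasts (models 10, 11, 14 and 15) with the treatment-path composition of each severity group.

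Making the End-of-Study models supportive is an option for the sponsor, not a requirement.

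The cost is a revised table, some SAP wording and a small amount of extra analysis, with no added participants. The downside is that the stated figures for the moderate-to-severe contrasts become less favourable.

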14.1 Source Data

Source documents and source data are considered to be the original documentation where participant information, visit consultations, examinations and other information are recorded. Documentation of source data is necessary for the reconstruction, evaluation and validation of clinical findings, observations, and other activities during a clinical trial.

14.2 Access to Source Data

The site investigators and site staff will make all source data available to the DAIT/NIAID and authorized representatives of DAIT/NIAID. Authorized representatives are bound to maintain the strict confidentiality of medical and research information that may be linked to identified individuals.

15 Quality Assurance and Quality Control

The investigator is required to keep accurate records to ensure that the conduct of the study is fully documented. The investigator is required to ensure that all CRFs are completed for every participant entered in the trial.

The sponsor is responsible for regular inspection of the conduct of the trial, for verifying adherence to the protocol, and for confirming the completeness, consistency, and accuracy of all documented data.

The CRFs will be completed online via a web-based electronic data capture (EDC) system that has been validated and is compliant with Part 11 Title 21 of the Code of Federal Regulations (CFR). Study staff at the site will enter information into the eCRFs, and the data will be stored remotely at a central database. Data quality will be ensured through the EDC system's continuous monitoring of data and real-time detection and correction of errors. All elements of data entry (i.e., time, date, verbatim text, and the name of the person performing the data entry) will be recorded in an electronic audit trail to allow all changes in the database to be monitored and maintained in accordance with federal regulations.

16 Protocol Deviations

16.1 Protocol Deviation Definitions

16.1.1 Protocol Deviation

The investigators and site staff will conduct the study in accordance with the protocol; no deviations from the protocol are permitted. Any change, divergence, or departure from the study design or procedures constitutes a protocol deviation. As a result of any deviation, corrective actions will be developed by the site and implemented promptly.

16.1.2 Major Protocol Deviation (Protocol Violation)

A Protocol Violation is a deviation from the IRB approved protocol that may affect the participant's rights, safety, or well-being and/or the completeness, accuracy, and reliability of the study data. In addition, protocol violations include willful or knowing breaches of human participant protection regulations or policies; any action that is inconsistent with the NIH Human Research Protection Program's research, medical, and ethical principles; and any serious or continuing noncompliance with federal, state, local or institutional human participant protection regulations, policies, or procedures. Examples of Major Protocol Deviations are described in the study MOP.

16.1.3 Non-Major Protocol Deviation

A non-major protocol deviation is any change, divergence, or departure from the study design or procedures of a research protocol that does not have a major impact on the participant's rights, safety or well-being, or the completeness, accuracy, and reliability of the study data.

16.2 Reporting and Managing Protocol Deviations

The study site PI has the responsibility to identify, document and report protocol deviations as directed by DAIT/NIAID. However, protocol deviations may also be identified during site monitoring visits or during other forms of study conduct review.

Upon determination that a protocol deviation has occurred, the study staff will a) notify the site PI, b) notify the SACCC and c) will complete a Protocol Deviation form. The protocol deviation form will document at minimum the date the deviation occurred, the date it was identified, a description of the event, whether the deviation resulted in an SAE/AE, PI signature (if major), IRB report requirement, and documentation of a corrective action plan. DAIT/NIAID may request discussion with the site PI to determine the effect of the protocol deviation on the study participant and his/her further study participation, the effect of the protocol deviation on the overall study, and corrective actions. The PI will electronically sign Major Deviations in the EDC, and submit the deviation to the central IRB, and local IRB/EC per IRB regulations. Major protocol deviations will be reported to the NIAID Allergy and Asthma DSMB by the DAIT/NIAID Medical Monitor at the medical monitor's discretion.

17 Ethical Considerations and Compliance with Good Clinical Practice

